1.0 Objectives

1.1 Describe the purpose, specific aims, or objectives of this research.

Response: The proposed research will translate research on delay discounting to the prevention of Type 2 diabetes (T2D) in persons with prediabetes. In this study, we will test our ability to engage and change the target, delay discounting (DD).

1.2 State the hypotheses to be tested, if applicable.

NOTE: A hypothesis is a specific, testable prediction about what you expect to happen in your study that corresponds with your above listed objectives.

Response: We predict that poverty conditions will increase discounting of the future for ERT subjects, but those receiving EFT will show levels of DD similar to levels observed for participants in the neutral condition. We also predict that EFT will activate brain regions associated with delay of gratification and prospection, and improve executive functions related to EFT, such as working memory.

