2.0 Scientific Endpoints

2.1 Describe the scientific endpoint(s), the main result or occurrence under study.

*NOTE: Scientific endpoints are outcomes defined before the study begins to determine whether the objectives of the study have been met and to draw conclusions from the data. Include primary and secondary endpoints. Some example endpoints are: reduction of symptoms, improvement in quality of life, or survival. Your response should **not** be a date.*

Response: The primary endpoint is the reduction of discounting of the future and increase activation in regions associated with delay of gratification and prospection.

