4.0 Study Design

4.1 *Describe and explain the study design (e.g. case-control, cross-sectional, ethnographic, experimental, interventional, longitudinal, observational).*

Response: This study is an experimental between-subjects design; subjects in the behavioral arm will be randomized to poverty/neutral scenarios crossed with EFT/ERT in a 2 x 2 factorial design. Subjects in the fMRI arm will be randomized to one of two groups: episodic future thinking (EFT) versus episodic recent thinking (ERT) control.

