17.0 Data Management and Analysis

17.1 Describe the data analysis plan, including any statistical procedures. This section applies to both quantitative and qualitative analysis.

Response:

Analytic plan is to use factorial ANCOVA to compare between group differences in different measures of DD, executive function and fMRI-measured brain function for subjects randomly assigned to poverty/neutral conditions and EFT/ERT. Covariates will be used if significant differences between groups are observed in subject characteristics. We predict a main effect of neutral/poverty, such that those assigned to poverty will have higher DD than those assigned to neutral, and an interaction between poverty/neutral and EFT such that in the poverty condition, EFT will reduce the discounting to levels achieved by the wealth, ERT subjects. We also predict when participants who receive EFT under challenge of poverty that EFT will increase activation in brain regions associated with delay of gratification (LPFC and AC) and prospection (hippocampus) relative to those who receive EFT under similar challenges.

17.2 If applicable, provide a power analysis.

NOTE: This may not apply to certain types of studies, including chart/records reviews, survey studies, or observational studies. This question is asked to elicit whether the investigator has an adequate sample size to achieve the study objectives and justify a conclusion.

Response:

The sample size is based on our studies of EFT versus ERT on DD in overweight and obese subjects, which showed an average AUC of $0.54 + 0.28$, and our unpublished research that poverty simulations reduces DD by 34%. We estimate in the ERT condition, neutral simulations will lead to less discounting and higher AUC than poverty simulations (0.54 vs 0.36). We estimate in EFT conditions, that simulations of neutral are associated with a small improvement in discounting in comparison to poverty simulations (0.63 vs 0.54). These predictions suggest that DD in EFT/Poverty and ERT/Wealth will be equivalent. The effect size for this interaction is 0.35. Using the overall SD we observed of 0.28, alpha of .05 and power of 0.80, we can show the effect size for this interaction with 17 Ss/group, or 68 total, or 34 per site in the behavioral portion and in the imaging portion. To be conservative, we will study up to 100 subjects.

17.3 Describe any procedures that will be used for quality control of collected data.

Response:

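### For delay discounting, no EFT-versus-ERT contrast is predicted, designated primary or powered; the only EFT term predicted and sized is the scenario-by-EFT interaction, which does not test the endpoint

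*Combined protocol and SAP*

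**What the plan says.** Section 1.1 gives the aim as engaging and changing delay discounting. Section 2.1 has two parts and names no contrast: "The primary endpoint is the reduction of discounting of the future and increase activation in regions associated with delay of gratification and prospection".

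Hypothesis 1.2 predicts that poverty raises discounting under ERT, and that EFT recipients stay near the level seen in the neutral condition.

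In 4.1 the behavioral arm is "randomized to poverty/neutral scenarios crossed with EFT/ERT in a 2 x 2 factorial design". For imaging: "Subjects in the fMRI arm will be randomized to one of two groups: episodic future thinking (EFT) versus episodic recent thinking (ERT) control".

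Section 17.1 begins: "Analytic plan is to use factorial ANCOVA to compare between group differences in different measures of DD, executive function and fMRI-measured brain function", with poverty/neutral and EFT/ERT as the two factors. For discounting it then makes two predictions. The first is "We predict a main effect of neutral/poverty, such that those assigned to poverty will have higher DD than those assigned to neutral". The second is an interaction, described as EFT under poverty bringing discounting to the level of the ERT subjects in the non-poverty condition (there called wealth). It also predicts that EFT increases activation, although the comparator is printed as EFT.

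Section 17.2 attributes an effect size of 0.35 to the interaction and concludes: "we can show the effect size for this interaction with 17 Ss/group", giving 68 in total, with up to 100 to be studied.

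**The concern.** The poverty main effect concerns the challenge, not the intervention. That leaves the interaction as the only term involving EFT that is both predicted for discounting and used for sizing. An interaction compares two EFT effects with each other. It does not ask whether either of them differs from zero.

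Two statements in the plan can therefore be true while the interaction is null: that EFT reduces discounting (2.1), and that EFT under poverty reaches the ERT/neutral level (1.2 and 17.1). With several discounting measures, two factors and an interaction, and no contrast designated, the choice of which EFT result answers the endpoint is left until the data are in. The stated 80% power also gives no information about the chance of detecting an EFT effect on discounting.

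**Working it through.** **Inputs (17.2).** Mean AUC (higher means less discounting): ERT/neutral 0.54, ERT/poverty 0.36, EFT/neutral 0.63, EFT/poverty 0.54. SD 0.28, alpha 0.05, 17 per cell (68) or 25 per cell (100). Assumed here: two-sided test, equal cells, common SD, no gain from covariates, no dropout.

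**The plan's own figure.** With Cohen's f = 0.35 on 1 degree of freedom and four cells, the noncentral F gives N = 67 for 80% power, rounded up to 68 (17 per cell); power at 68 is 0.811. So 68 reproduces from 0.35. The 0.35 itself is the f for the spread of all four cell means. Their mean is 0.5175, the squared deviations sum to 0.038475, and √(0.038475/4)/0.28 = 0.350. The interaction f is 0.09/(4 × 0.28) = 0.080. That mis-sizing is a separate issue. It matters here only because it is why the interaction's power below is not 80%.

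**EFT contrasts on the plan's means.**
- EFT gain in poverty: 0.54 − 0.36 = 0.18.
- EFT gain in neutral: 0.63 − 0.54 = 0.09.
- EFT main effect: (0.18 + 0.09)/2 = 0.135 (d = 0.135/0.28 = 0.48).
- Interaction: 0.18 − 0.09 = 0.09.

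**Standard errors, with n per cell.** Main effect 0.28 × √(1/n); within poverty 0.28 × √(2/n); interaction 0.28 × √(4/n). The interaction's standard error is twice that of the main effect.

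**Power (noncentral t, N − 4 degrees of freedom).**

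| Contrast | Size | SE at 68 | Size/SE at 68 | Power at 68 | SE at 100 | Size/SE at 100 | Power at 100 |
|---|---|---|---|---|---|---|---|
| EFT main effect | 0.135 | 0.0679 | 1.99 | 50% | 0.0560 | 2.41 | 67% |
| EFT vs ERT within poverty | 0.18 | 0.0960 | 1.87 | 45% | 0.0792 | 2.27 | 61% |
| Interaction | 0.09 | 0.1358 | 0.66 | 10% | 0.1120 | 0.80 | 13% |

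For 80% power the main effect needs about 138 subjects in total.

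**Can the prediction hold with a zero interaction?** Keep the ERT means and let EFT add 0.18 in both scenarios. This is hypothetical, not the plan's assumption. EFT/poverty is 0.36 + 0.18 = 0.54, exactly the ERT/neutral mean, as 1.2 and 17.1 predict. EFT/neutral is 0.54 + 0.18 = 0.72. The interaction is (0.54 − 0.36) − (0.72 − 0.54) = 0, so its test rejects 5% of the time. The EFT main effect of 0.18 would have 74% power at 68 and 89% at 100.

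**Imaging arm.** As 4.1 describes it, this arm has only the EFT/ERT factor. Neither predicted discounting term can be estimated there, whereas EFT versus ERT can.

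**The case against.** The strongest reply is that the ANCOVA already has EFT/ERT as a factor, so its main effect will be estimated and tested whether or not it appears among the predictions. This is correct. A reader might infer that the plan contains no EFT-versus-ERT test at all, and 17.1 does not support that. What remains is that a term available in a model is not a designated or powered test of an endpoint.

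Second, 1.2 is a buffering hypothesis, in which poverty raises discounting and EFT offsets it, so interest in the poverty condition is deliberate. This also stands, and it makes EFT versus ERT within poverty a relevant contrast. It does not rescue the interaction, because the buffering pattern can be met with no interaction at all.

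Third, the endpoint's activation part does carry an EFT prediction in 17.1. The point is therefore confined to discounting.

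Fourth, a reader might infer that EFT is judged solely by the interaction, so that a null result would be declared a failure to engage the target. The documents contain no such decision rule and do not call the interaction primary.

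Finally, the main effect is itself underpowered at 68 and 100. That is true. Enrollment of up to 250 across sites is allowed (5.1, 29.3); if half were behavioral, which is an assumption, 125 subjects would give about 76%.

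**Conclusion.** The point holds for delay discounting. The plan has an EFT/ERT factor but predicts, designates and powers no EFT-versus-ERT contrast. The one EFT term it does predict and size answers a different question from 2.1 and is not needed for the pattern in 1.2. On the plan's own means that term has roughly one chance in eight to ten of reaching significance. The contrasts that do address the endpoint and the hypothesis have between 45% and 67% across the two sample sizes.

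It would go too far to say that the plan expects a zero interaction. Its means imply a gain of 0.18 in poverty and 0.09 in neutral, hence an interaction of 0.09. The zero-interaction case, with its 74% and 89%, shows what is possible and is not a forecast. All powers rest on the assumptions listed with the inputs. The mis-sized 0.35 should be raised once, separately, and not counted again here.

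**What to change.** In 17.1:
- Designate the EFT-versus-ERT difference in AUC from the same ANCOVA, averaged over scenario, as the test of the discounting endpoint in 2.1.
- Report EFT versus ERT within poverty as the direct test of hypothesis 1.2.
- Keep the scenario-by-EFT interaction as the question of whether the benefit differs by scenario.

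In 17.2, state the power of these contrasts on the plan's own means: about 50% at 68 and 67% at 100 for the main effect, and about 45% and 61% within poverty.

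The edits are to wording and need no new measurements or model. The cost is that the stated power falls below 80% and the interaction is no longer the headline test. If the sponsor wants 80% for the main effect on these means, about 138 behavioral subjects are needed, which is a decision about enrollment and not only about text.

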Subjective Hunger: Participants will be asked to provide subjective ratings of their hunger. Hunger will be assessed using a 5-point Likert scale (anchored by 1-Extremely Full and 5-Extremely Hungry).

Subjective Preferences: Participants may be asked to provide subjective ratings of their food/activity preferences by ranking, rating their liking using a 5-point Likert scale (anchored by 1-Do not like and 5-Like very much), and making choices between their food/activity.

Same Day Food Recall: Participants will be asked if they are willing to eat the study food during a 24-hour recall questionnaire assessing past food behavior

(e.g. what time they ate their last meal, food items consumed in the past 24 hours, etc.). Those who say they are not willing to eat the study food will not be included in the study.

Cue Attention: A Likert-style scale assessing attentiveness to the episodic cues and vividness cues during tasks will be assessed on a scale from 1 to 5, where 1 indicates “not at all” and 5 indicates “very much”.

Delay Discounting: An operational definition of impulsivity is delay discounting, the degree to which a person will discount the value of a larger delayed reward in favor of a smaller immediate reward. Computerized/ experimenter administered assessments will provide participants with choices between a smaller amount of a hypothetical commodity available immediately or a larger amount available later. Participants will make choices between rewards such as money, food, physical activity, and health gains. Two methods will be used to measure discounting, Adjusting Amount and Adjusting Delay.

Adjusting Amount Discounting. The magnitude of the immediate commodity is adjusted until it is subjectively equivalent to the later larger amount. Subjective equivalence will be obtained at delays such as; 1 day, 1 week, 1 month, 3 months, 6 months, and 1 year. To ensure comparison between money and non-monetary rewards, prior to running the discounting programs for food, physical activity and health, participants will indicate the amount of the commodity whose receipt “right now” would be equally valuable to the participants as receiving a set amount of money, for example \$100.

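### Sections 17.1 and 17.2 tie the prediction that EFT brings poverty-condition discounting to the ERT/neutral level to the poverty x EFT interaction, and declare no cell contrast that would test it

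*Combined protocol and SAP*

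**What the plan says.** The poverty/neutral cells exist only in the behavioral arm. Section 4.1 states that "subjects in the behavioral arm will be randomized to poverty/neutral scenarios crossed with EFT/ERT in a 2 x 2 factorial design".

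Section 1.2 gives the EFT prediction on discounting: under poverty, "those receiving EFT will show levels of DD similar to levels observed for participants in the neutral condition". Section 17.1 restates it as an "interaction between poverty/neutral and EFT such that in the poverty condition, EFT will reduce the discounting to levels achieved by the wealth" ERT subjects. The method is a factorial model: "Analytic plan is to use factorial ANCOVA to compare between group differences in different measures of DD". The predictions for discounting in 17.1 are a poverty main effect and this interaction. No simple effect, cell contrast or equivalence test is declared.

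Section 17.2 assumes mean AUCs (higher means less discounting) of 0.54 for ERT/neutral, 0.36 for ERT/poverty, 0.63 for EFT/neutral and 0.54 for EFT/poverty, with SD 0.28. It adds: "These predictions suggest that DD in EFT/Poverty and ERT/Wealth will be equivalent". It calls 0.35 the effect size for the interaction and concludes that "we can show the effect size for this interaction with 17 Ss/group, or 68 total" at alpha .05 and power 0.80. It then allows up to 100 subjects.

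On the outcome, section 10.3 says "Two methods will be used to measure discounting, Adjusting Amount and Adjusting Delay", with several commodities.

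**The concern.** The prediction is about one cell reaching the level of another. The interaction asks something else: whether the poverty effect is smaller under EFT than under ERT. If the interaction is the only declared term carrying the prediction, two misreadings are open. A null interaction could be reported as EFT failing under poverty although EFT/poverty equals ERT/neutral. A positive interaction could be reported as the prediction met although EFT closes only part of the gap.

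The comparison that answers the question could still be made, but its status, its rank beside the main effects and interaction, and the discounting measure would be open to choice after the data are seen.

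**Working it through.** **Notation and inputs.** RN, RP, EN, EP stand for ERT/neutral, ERT/poverty, EFT/neutral, EFT/poverty. From 17.2: RN 0.54, RP 0.36, EN 0.63, EP 0.54; SD 0.28; alpha .05; 17 per cell. 'Wealth' is read as neutral, because ERT/neutral is the ERT cell with mean 0.54. Assumed here: equal cells, a two-sided test, no gain from covariates, and pooled error df = 4n - 4.

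**1. The plan's own figure.** An F test with 1 numerator df, N - 4 denominator df and noncentrality N x f², with f = 0.35, first exceeds 0.80 power at N = 67. Rounded to equal cells this is 68, with power 0.811. The stated 68 is reproduced.

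**2. What 0.35 represents.**
- Grand mean = (0.54 + 0.36 + 0.63 + 0.54)/4 = 0.5175.
- Mean squared deviation = (0.00051 + 0.02481 + 0.01266 + 0.00051)/4 = 0.00962.
- Omnibus f = √0.00962 / 0.28 = 0.350.
- Interaction = (RN - RP) - (EN - EP) = 0.18 - 0.09 = 0.09, and its f = 0.09/(4 x 0.28) = 0.080.

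So 0.35 matches the spread of all four cells, not the interaction.

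**3. Power of the interaction.** SE = 0.28 x √(4/n), which is 0.136 at 17 per cell and 0.112 at 25. For a true value of 0.09, noncentral t power is 0.10 at 68 and 0.125 at 100. About 1,220 subjects in total would be needed for 80%.

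**4. The level claim is a different contrast.** In the order RN, RP, EN, EP, the level claim EP - RN has coefficients (-1, 0, 0, 1) and the interaction has (1, -1, -1, 1). Their product sums to -1 + 0 + 0 + 1 = 0, so with equal cells the two estimates are uncorrelated. Two sets of means show that neither implies the other:

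| RN / RP / EN / EP | Interaction | EP - RN | EP - RP |
|---|---|---|---|
| 0.54 / 0.36 / 0.63 / 0.54 (plan) | 0.09 | 0 | 0.18 |
| 0.54 / 0.36 / 0.72 / 0.54 | 0 | 0 | 0.18 |
| 0.54 / 0.36 / 0.54 / 0.45 | 0.09 | -0.09 | 0.09 |

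In the second row the level claim holds exactly, yet the interaction test rejects in 5% of trials at any sample size. In the third row the interaction is the plan's own 0.09, but the 0.18 gap is only half closed.

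**5. The direct contrasts.** SE of a difference between two cells = 0.28 x √(2/n).

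| Behavioral-arm total | n per cell | SE | Power, EP - RP = 0.18 |
|---|---|---|---|
| 50 (assumed) | 12.5 | 0.112 | 0.35 |
| 68 | 17 | 0.096 | 0.455 |
| 100 | 25 | 0.079 | 0.614 |
| 124 (assumed) | 31 | 0.071 | 0.709 |
| 156 | 39 | 0.063 | 0.805 |

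At 38 per cell power is 0.795, so 39 is the smallest n per cell reaching 80%. For EP - RN the 95% confidence half-width is 0.19 at 68 and 0.16 at 100, against an assumed whole poverty effect of 0.18.

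**6. Why several totals.** Section 17.2 does not say whether 100 is for the behavioral portion or for both portions together; 50 takes it as the total, split evenly. Sections 5.1 and 29.3 allow up to 250 overall; 124 is about half of that in four equal cells.

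**The case against.** The strongest reply is that the gap is one of declaration only. Sections 17.1 and 17.2 write down both cells, and the planned ANCOVA contains everything needed: EP - RP equals the EFT main effect plus half the interaction (0.135 + 0.045 = 0.18), and EP - RN equals the EFT main effect minus the poverty main effect (0.135 - 0.135 = 0). In the half-closed example the EFT main effect falls to 0.045 against 0.135 planned, so a careful reader of all terms would notice. One may also say that 17.1 predicts an interaction and a level pattern together, so reporting an absent interaction as absent would be correct.

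Most of this stands. The model is adequate and the cells are identifiable. It does not remove the need to say which combination tests the prediction. The EFT main effect alone does not isolate the poverty cell: means of 0.54/0.36/0.72/0.45 keep it at 0.135 while the gain under poverty is 0.09. In fairness, the interaction there is -0.09, the reverse of the prediction, so the two terms read together would give warning.

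Three stronger readings are not supported:
- A reader might infer from 1.2 that the neutral comparator is undefined. Sections 17.1 and 17.2 identify it as the ERT cell.
- A reader might infer that the plan relies on an equivalence test without a margin. It declares none; the wording in 17.2 describes two assumed means of 0.54.
- A reader might infer that the discounting measure is wholly open. Section 17.2 uses AUC and 10.3 ties k-values to the adjusting-delay task, which points to the adjusting-amount task. The commodity is not stated in 17.2.

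**Conclusion.** The concern holds as a missing declared contrast, not as a missing comparison or a wrong model. The plan attaches a statement about cell levels to a term that is orthogonal to it when cells are equal. On its own means that term has about 10% power at 68 and 13% at 100. Following the plan as written would therefore usually give a null interaction even if all of 17.2 were true.

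The direct test of EFT under poverty is far better powered, though still below the plan's 0.80 target at every arm size considered short of 156. These figures rest on the 17.2 means and SD, equal cells, two-sided 0.05 and no covariate gain. A covariate that explains outcome variance would raise the powers somewhat. The orthogonality does not depend on the means or SD. The data can still answer the question if the contrasts are fixed beforehand.

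**What to change.** In 17.1, for the behavioral arm and the AUC measure used in 17.2 (with its commodity named), prespecify from the same ANCOVA:

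1. EFT/poverty minus ERT/poverty, 1 df, two-sided 0.05, as the test that EFT reduces discounting under poverty. Fix its place relative to the main effects and interaction beforehand, for example as the single confirmatory test of this prediction with the others supporting. If more than one is confirmatory, state the order or the alpha split.
2. EFT/poverty minus ERT/neutral, as an estimate with its confidence interval, with no claim of equivalence unless a margin is fixed beforehand.

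In 17.2, state the power of contrast 1 for the behavioral-arm size actually intended, using the table above. The planned main effects and interaction stay.

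No extra subjects, visits or measures are required. The cost is candour: the plan must say that its direct test falls below 0.80 power, or that 39 per cell (156 in the behavioral arm) would be needed to reach it. As optional tidying, 1.2 could name the ERT/neutral cell, and 17.2 could say that the two cells are assumed to have equal means.

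### The plan predicts that EFT under poverty will match neutral ERT, but it plans only difference tests with no margin, so it has no valid route to that conclusion

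*Combined protocol and SAP*

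**What the plan says.** Three places in the combined protocol and SAP predict sameness.

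- Section 1.2 (hypotheses): under poverty, "those receiving EFT will show levels of DD similar to levels observed for participants in the neutral condition".
- Section 17.1 (analysis plan): in the poverty condition, "EFT will reduce the discounting to levels achieved by the wealth, ERT subjects". The neutral cell is printed here as wealth.
- Section 17.2 (power analysis): "These predictions suggest that DD in EFT/Poverty and ERT/Wealth will be equivalent". This follows assumed mean AUCs of 0.54 (neutral) and 0.36 (poverty) under ERT, and 0.63 (neutral) and 0.54 (poverty) under EFT.

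The method is given once, in section 17.1: "Analytic plan is to use factorial ANCOVA to compare between group differences in different measures of DD", along with executive function and brain measures. The sample size rests on "The effect size for this interaction is 0.35" and "Using the overall SD we observed of 0.28, alpha of .05 and power of 0.80". It comes to 17 per group, 68 in total, with up to 100 to be studied. No section gives an equivalence or non-inferiority margin, an equivalence test, or a confidence-interval rule for what counts as similar.

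**The concern.** A test of differences can show that two cells differ. It cannot show that they are the same. The prediction about EFT/poverty against neutral ERT needs a statement of how large a gap would still count as the same, and a rule that excludes larger gaps. The plan has neither.

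The tests it does imply answer other questions. The interaction asks whether the poverty effect differs between EFT and ERT. A comparison of EFT with ERT inside poverty asks whether EFT helps there. Both can be positive when EFT closes only part of the poverty deficit. At stake is the difference between two reports: that EFT reduces discounting under poverty, and that EFT brings it back to the neutral level. The second is the stronger claim, and nothing in the plan would support it.

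**Working it through.** **Inputs.** From section 17.2: the four cell means above, SD 0.28, alpha .05, 17 per group, up to 100 subjects. From section 4.1: a 2 x 2 design in the behavioral arm. Assumed: two-sided testing (not stated), equal cells, error pooled over four cells (df = 4n − 4). Taking all 100 subjects in one portion gives 100/4 = 25 per cell. Higher AUC means less discounting.

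**1. The plan's own figure.** With f = 0.35, one numerator df, four cells, alpha .05 and 80% power, the noncentral F gives N = 67, hence 68 or 17 per cell (power 0.81). The stated size reproduces from the stated effect size. It is sized to detect a difference and says nothing about equivalence.

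**2. Precision of the relevant gap (EFT/poverty minus ERT/neutral).** SE = 0.28 × √(2/n); half-width = t × SE.

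| n per cell | SE | t | 95% CI half-width |
|---|---|---|---|
| 17 | 0.0960 | 1.998 | 0.192 |
| 25 | 0.0792 | 1.985 | 0.157 |

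The assumed poverty effect is 0.54 − 0.36 = 0.18. At 17 per cell, an observed gap of exactly zero would leave the whole deficit inside the interval. At 25 it would leave 0.157/0.18 = 87% of it.

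**3. The interaction does not identify full repair.** On the plan's means the contrast is (0.54 − 0.36) − (0.63 − 0.54) = 0.09. Suppose instead that EFT repairs half the deficit (EFT/poverty 0.36 + 0.09 = 0.45) and leaves EFT/neutral at 0.54. The contrast is (0.54 − 0.36) − (0.54 − 0.45) = 0.09, the same value. The interaction test cannot tell these two situations apart.

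**4. Nor does a significant benefit within poverty.** Simulation of the cells with the inputs above:

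| True EFT/poverty AUC | n per cell | Significant benefit within poverty | That benefit and no significant gap from neutral ERT | No significant gap, given a significant benefit |
|---|---|---|---|---|
| 0.45 (half repair) | 17 | 15% | 14% | 96% |
| 0.45 (half repair) | 25 | 20% | 19% | 95% |
| 0.54 (full repair) | 17 | 45% | 43% | 95% |
| 0.54 (full repair) | 25 | 61% | 59% | 95% |

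The joint pattern is more common under full repair only because the benefit test is more often significant. Once that benefit is seen, the absence of a gap adds almost nothing.

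**5. If non-significance alone were taken as sameness.** With no EFT effect the true gap is 0.18. From the noncentral t, the chance of no significant gap is 54.5% at 17 per cell (53% to 56% depending on the error term and approximation) and about 39% at 25.

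**6. A margin rule, for illustration.** Let similar require the lower 95% limit of the gap to exceed −0.09, half of 0.18. At true equality, power = P(T > t), with T noncentral t and noncentrality 0.09/SE. This gives about 15% at 17 per cell and 20% at 25. The observed gap would have to exceed 0.192 − 0.09 = 0.102 or 0.157 − 0.09 = 0.067 in favour of EFT/poverty.

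**The case against.** The documents state a prediction, not a decision rule. They never say that a non-significant EFT/poverty versus ERT/neutral comparison will count as success, and they do not name that comparison as a test. In section 17.2 the word equivalent describes assumed inputs, since both cells are set at 0.54. Section 2.1 defines the primary endpoint as a reduction in discounting together with increased brain activation, which is a claim about differences. All of this stands.

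A reader might infer that the plan would announce its predicted result more than half the time with a useless EFT. The documents do not support that. The predicted pattern also includes an interaction. With no EFT effect at 17 per cell, a non-significant gap plus a significant interaction in the predicted direction occurs about 1.3% of the time. A non-significant gap plus a significant EFT benefit within poverty occurs about 2.2% of the time. Seventeen per cell is also the computed minimum. Section 29.3 allows up to 250 subjects; split over two arms and four cells that is about 31 per cell, where the figure in step 5 falls to about 29%.

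These safeguards work against a useless EFT, not against a partly effective one. The interaction is also hard to find: the 0.09 contrast implied by the plan's own means has power of about 10% at 68 subjects and 12.5% at 100. Interpretation may therefore rest on cell comparisons even if every assumption is right.

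**Conclusion.** The point holds as a gap between hypothesis and method. The plan predicts sameness in three places and provides no analysis that can show it. Steps 3 and 4 give the size: full and half repair can produce the same interaction, and after a significant within-poverty benefit a non-significant gap from neutral ERT is about equally likely under either (95% to 96%).

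Two stronger readings are not supported. One is that the plan will treat non-significance as equivalence; the 55% and 39% in step 5 apply only under that rule, which the documents do not state. The other is that a useless or half-effective EFT would usually be reported as restoring neutral levels. Under half repair, a significant benefit with no significant gap occurs in only 14% (17 per cell) or 19% (25 per cell) of trials.

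The figures rest on the plan's means and SD, two-sided .05, equal cells and pooled error. The −0.09 margin is illustrative, since the documents give no basis for any margin. The change should be made before analysis.

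**What to change.** **Section 17.1.** State that a non-significant difference will not be read as equivalence. Name the EFT/poverty minus ERT/neutral AUC difference and report it with its 95% CI. Allow wording that EFT/poverty is similar to, or reaches, the neutral level only if the lower confidence limit lies above a margin that the sponsor chooses in advance and that is smaller than the assumed poverty effect of 0.18. A margin of −0.09 would serve as an illustration, with the low power shown in step 6 stated openly.

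**Sections 1.2 and 17.2.** Replace the sameness wording with estimation wording, and say that the sample is not sized to show equivalence (half-width about 0.19 AUC at 17 per cell, 0.16 at 25).

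**Cost.** Text changes and one confidence interval, with no added subjects or data. The small downside is that the trial will probably have to conclude that EFT reduces discounting under poverty, not that it restores neutral levels.
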